3.5 Quality of Life Questionnaire

Quality of life will be captured using the Atrial Fibrillation Effect on Quality of Life (AFEQT) questionnaire. It is a standardized, disease-specific, reliable and responsive measure of health-related quality of life in patient with AF (17). The AFEQT is a self-reported questionnaire with responses on a 7-point Likert scale. The 20-item instrument is divided into three domains (4-item symptom score, 8-item daily activities score, 6-item treatment concerns score) plus two treatment satisfaction questions. The domains symptoms, daily activities and treatment can be aggregated into an overall score.

The AFEQT has been developed as a self-administered questionnaire for patients with AF. Reading and understanding the questionnaire in the applied language is mandatory when completing the instrument (18). The AFEQT questionnaires should preferably be signed off by the patient, but if it is not possible to obtain the signature of the patient, it is accepted that a member of the site study team signs and dates the questionnaire to confirm their validity. If the questionnaire is administered by phone, the person conducting the follow up call should sign off the questionnaire.

The validated languages cover the following: French, German, Italian, Spanish (Spain), Polish and Dutch, Korean. The AFEQT questionnaire will be applied to all patients, either in the linguistically validated country-specific version or, if a country-specific validated version does not exist, in the not validated version translated into the local language of the respective patients according to local requirements and regulations. To avoid possible confounders, all analyses regarding the AFEQT questionnaire will be performed for the overall sample and stratified by validated vs not validated version.

This also applies to the mode of questionnaire administration: In general, the AFEQT questionnaire will be filled in by the patient himself. However, in some sites the AFEQT questionnaire will be administered by telephone interview. To avoid possible confounders, all analyses regarding the AFEQT questionnaire will be performed for the overall sample and stratified by self-administered vs administered by telephone interview.

The license for using the questionnaire in local languages of participating countries will be obtained and submitted under the request.

It is recommended that the questionnaire be completed at baseline and at 12 months FU. At baseline AFEQT can be completed starting from 14 days prior to the hospitalization for the index Phased RFA procedure if patient consent his/her participation in the registry.

3.6 Participating Sites

Approximately 38 sites in 13 countries (Germany, Netherlands, United Kingdom, Hungary, Italy, Spain, Switzerland, Israel, Poland, Portugal, France, Greece and South Korea) are anticipated to take part in the registry. Centers in other countries may be added during the study as well as listed countries can decline participation during the study. The list of participating sites will be updated and distributed under the separate cover.

Site eligibility for participation includes hospital-based physicians treating AF patients with Phased RFA technology.

Prior to performing study-related procedures, the site must have ethical committee (EC)/institutional review board (IRB) and associated regulatory authority approval, if applicable (e.g. Competent Authority approval), sign Clinical Trial Agreement as well as receive documentation from Medtronic or delegated CRO confirming the site readiness.

3.6.1 Site selection

The site should have adequate resources, facilities and equipment needed to follow the clinical investigational plan (CIP). The patient population should be adequate to make a contribution to the study.

Sites must have employed at least one English-speaking person, who will participate in the study and be available for all study related communication, e.g. email communication, possibly remote monitoring (see chapter 7.5.). Additionally, sites must acknowledge and agree to comply with applicable regulatory and local requirements governing clinical study conduct.

Sites will not be preselected by experience working with Phased RFA technology and RFA utilization in general. To take different sites characteristics into consideration the sites will be asked to specify their experience with Phased RFA during three years prior to enrollment as well as average range of overall RFA per year in a short site questionnaire before starting the enrollment.

The role of the PI is to implement and manage the day-to-day conduct of the clinical investigation in addition to ensuring data integrity and the rights, safety and well-being of the patients involved in the clinical investigation.

3.6.2 Site activation

During the activation process (prior to patient enrollment), Medtronic or CRO will train site personnel on the clinical investigational plan (CIP), relevant standards and regulations, patient informed consent/patient data release form (PIC/PDRF), and on data collection and reporting tools. The site activation can be conducted in person, via telephone or remote video conference.

Sites are required to notify Medtronic of the addition of new hospital staff involvement in the study, including notification of appropriate changes in the Delegation Task Log. New study participants should be trained on the applicable study requirements relevant to their role before contributing into the clinical study. It is the site PI's responsibility, that new study personnel are comprehensively trained with regards to GOLD AF registry requirements. Trainings of all participants will be documented and signed in the Training Log file.

Prior to performing study related activities, all local regulatory requirements shall be fulfilled, including, but not limited to the following:

- EC/IRB approval (and voting list, as required by local law) of the current version of the CIP and PIC/PDRF
- Regulatory authority approval or notification (if required per local law)
- Fully executed Clinical Trial Agreement (CTA)
- Curriculum Vitae (CV) of PIs
- Documentation of delegated tasks in the Delegation Task Log
- Documentation of study training in the Site Training Log

In order to obtain database access details, the database User Account Request Form should be signed by personnel delegated to work with eCRF. A scanned copy needs to be sent to the sponsor or designee.

Additional requirements imposed by the EC/IRB and regulatory authority shall be followed, if appropriate. Medtronic or CRO will provide each study center with documentation of study center/investigator readiness; activation letter must be received prior to patient enrollment.

4 Statistical Methods and Planned Analysis

This section describes the most relevant parts of the statistical analyses planned for this registry. All planned statistical methods will be described in detail in the Statistical Analysis Plan (SAP), which will be finalized prior to the first database freeze lock.

In general, this registry is intended to collect data under real life conditions. The statistical analysis will be performed in explorative and descriptive manner, i.e. no pre-specified hypothesis testing.

4.1 Registry Population

Data from all patients who are enrolled in the study (patients who meet the eligibility criteria and have signed the PIC/PDRF) will be included in the analysis. If a patient exits from the study, data collected prior to the study withdrawal will be included in the analysis.

4.2 Missing Data

In order to assess the effects of patients lost to follow up, percentages of dropouts will be summarized. In addition, baseline characteristics of patients who were lost to follow up in comparison to patients with a complete follow up will be described.

All reasonable attempts will be undertaken to ensure completeness of data collection in this registry. Before database lock, as many queries as possible will be cleared.

Missing data will not be imputed.

4.3 Sample size considerations

The sample size determination has been based on chronic efficacy, freedom from AF recurrence at 12 months. The sample size calculation is based on the main objective to document real-life mid-term efficacy of patients with atrial fibrillation who have undergone Phased RFA. Efficacy in this case is assumed as the proportion of AF recurrence within 12 months following the index procedure.

The table below shows the sample size needed for estimating a binomial proportion for given prevalence with corresponding precision.

Table 4-1: Table for precision and prevalence for sample size assessment.

| Prevalence | Precision | | | |
|------------|-----------|------|-----|-----|
| | 1% | 2.5% | 5% | 10% |
| 0.1 | 4150 | 665 | 167 | 42 |
| 0.2 | 7377 | 1181 | 296 | 75 |
| 0.3 | 9682 | 1550 | 388 | 98 |

Precision = half-width of a 95% Confidence Interval (CI)

Design effect = 1.2 (variance inflation due to cluster sampling design)

Low sampling rate assumed to have no impact on sample size calculation

Assuming a prevalence of 20% of re-ablations 12 months after treatment, a sample size of 800 will allow the study to estimate the prevalence with a given precision of $\pm 3.8\%$ [range of 95%-CI: 7.6%]. This size guarantees enough information for estimating the prevalence in smaller subgroups (e.g. subgroup with a prevalence of 25% with a precision of $\pm 6.6\%$ [range of 95%-CI: 13.3%]).

A drop-out rate of 25% is assumed, i.e. an estimated drop-out rate of 200 patients. Therefore, it is planned to enroll a total number of patients of approximately 1000.

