### 3.3 Sample Size Determination

The sample size calculation is based on the main objective to document real life mid-term efficacy of patients with atrial fibrillation who were scheduled for phased RF ablation. Efficacy is in this case assumed as the proportion of redo ablations 12 months after treatment.

The table below shows the sample size needed for estimating a binomial proportion for given prevalence with corresponding precision.

**Table 1:** Cross table for precision and prevalence for sample size assessment.

Prevalence	Precision			
	1%	2.5%	5%	10%
0.1	4150	665	167	42
0.2	7377	1181	296	75
0.3	9682	1550	388	98

Precision = half-width of a 95% CI

Design effect = 1.2 (variance inflation due to cluster sampling design)

Low sampling rate assumed to have no impact on sample size calculation

Assuming a prevalence of re-ablation 12 months after treatment of 20%, a sample size of 800 will allow the study to estimate the prevalence with a given precision of  $\pm 3.8\%$  [range of 95%-CI: 7.6%]. This size guarantees sufficient information to estimate the prevalence in smaller subgroups (e.g. subgroup with a prevalence of 25% with a precision of  $\pm 6.6\%$  [range of 95%-CI: 13.3%]).

A drop-out rate of 25% is assumed (i.e. an estimated drop-out of about 200 patients). Thus, it is planned to enrol a total number of patients of at least 800 - 1000.

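### The stated ±3.8% for 800 patients does not follow from the plan's own inputs (±3.04%), a 25% drop-out is counted as 200 of 1000, and the precision is given for re-ablation rather than AF recurrence

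*Protocol*

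**What the plan says.** Protocol 4.3 and SAP 3.3 carry the same table of sample sizes by prevalence and precision. Precision is defined as half the width of the 95% interval, with this allowance: "Design effect = 1.2 (variance inflation due to cluster sampling design".

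Below the table the Protocol states: "Assuming a prevalence of 20% of re-ablations 12 months after treatment, a sample size of 800 will allow the study" to reach ±3.8% (width 7.6%). The SAP has the matching sentence: "Assuming a prevalence of re-ablation 12 months after treatment of 20%, a sample size of 800 will allow the study", with the same figures. Both add a subgroup example, a "subgroup with a prevalence of 25% with a precision of" ±6.6% (width 13.3%), without giving the subgroup's size.

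On losses the Protocol says: "A drop-out rate of 25% is assumed, i.e. an estimated drop-out rate of 200 patients", and then "it is planned to enroll a total number of patients of approximately 1000". The SAP also pairs 25% with about 200 patients, but in sections 3.1 and 3.3 it gives the target as a minimum of 800 to 1000.

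On the outcome, Protocol 4.3 says: "Efficacy in this case is assumed as the proportion of AF recurrence within 12 months following the index procedure". SAP 3.3 says instead: "Efficacy is in this case assumed as the proportion of redo ablations 12 months after treatment".

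For the main analysis, Protocol 4.4.1 and SAP 8.1.2 specify a Kaplan-Meier estimate at 12 months with Greenwood's standard error and a log-log 95% interval. Neither names an adjustment for site.

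**The concern.** The registry tests no hypothesis, so the attainable precision is the only justification for its size. That justification should be reproducible from its stated inputs and should refer to the quantity the study sets out to estimate.

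Here the headline precision conflicts with the table directly above it, and the drop-out percentage and count use different denominators. The precision also belongs to re-ablation, while the main endpoint adds cardioversion and documented or symptomatic AF (and, in the Protocol, left flutter and left atrial tachycardia). If the figures pass into the final report, readers will be given a precision and a loss allowance that cannot be checked.

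A smaller question is whether the clustering allowed for in planning should be visible in the main interval.

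**Working it through.** **Inputs** (Protocol 4.3, SAP 3.3): 95% interval, z = 1.96; design effect 1.2; prevalence 20%; n = 800; stated result ±3.8%, width 7.6%.

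**1. Reproduce the table.** n = 1.2 × z² × p(1−p)/e², rounded up before and after multiplying by 1.2. For p = 0.20 and e = 0.025: 1.96² × 0.16 / 0.025² = 983.4, rounded up to 984; 984 × 1.2 = 1180.8, rounded up to 1181, as printed. All 12 cells match in this way, so this is the plan's own formula.

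**2. Apply it to 800 patients.** Half-width = 1.96 × √(1.2 × 0.20 × 0.80 / 800) = 1.96 × √0.00024 = 3.04%, width 6.07%. Cross-check from the table: 2.5% × √(1181/800) = 3.04%.

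**3. Look for the source of 3.8%.** At p = 0.20, ±3.8% needs n = 1.2 × 1.96² × 0.16 / 0.038² ≈ 511, or at n = 800 a design effect of 0.038² × 800 / (1.96² × 0.16) ≈ 1.88. Other constructions at n = 800 and p = 0.20 also miss it:
- no design effect: 2.77%
- continuity correction: about 3.1%
- Wilson: 3.03%
- Clopper-Pearson at the effective n of 667: 2.97% below and 3.24% above
- 1.2 applied to the standard error: 3.33%
- 99% confidence: 3.99%

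A value of 3.80% does appear for p = 0.50 with n = 800, and for p = 0.25 with n = 600. Neither is the stated set, so the origin is unknown.

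**4. Subgroup.** At p = 0.25, ±6.6% solves to n = 1.2 × 1.96² × 0.1875 / 0.066² ≈ 198; n = 196 gives 6.64% and n = 200 gives 6.57%. The unstated size is about 195 to 200.

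**5. Drop-out.** 200/800 = 25%, but 200/1000 = 20%. At 25% loss, 1000 × 0.75 = 750 remain, and 800 evaluable would need 800/0.75 = 1067 enrolled. The planned 1000 equals 800 × 1.25. With 750, the half-width at 20% is 1.96 × √(0.192/750) = 3.14%.

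**6. Precision for AF recurrence**, design effect 1.2 and n = 750. The recurrence rates are assumptions; three are taken from the efficacy figures cited in Protocol 4.4.1.

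| Assumed recurrence | Basis | Half-width |
|---|---|---|
| 18.6% | cited paroxysmal success 81.4% | 3.05% |
| 26% | cited average efficacy 74% | 3.44% |
| 30% | highest row of the plan's table | 3.59% |
| 45.9% | whole cohort at the cited persistent success 54.1% | 3.91% |

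For example, 1.96 × √(1.2 × 0.26 × 0.74 / 750) = 3.44%. With n = 750, ±3.8% holds up to a recurrence of about 38%. If the SAP's lower figure of 800 were the number enrolled, 25% loss would leave 600: ±3.51% at 20% and ±3.84% at 26%.

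**7. Clustering.** If the design effect is 1.2, a Greenwood interval is 1/√1.2 = 0.913 of the width that planning implies, so about 9% too narrow. For S = 0.80, n = 800 and no censoring, the log-log interval is 77.1% to 82.6%. With effective n = 800/1.2 = 667 it is 76.8% to 82.8%. The lower limit moves by 0.30 points and the upper by 0.23.

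**The case against.** The strongest reply is that nothing in the results depends on these figures. The ±3.8% is conservative: at 20% it is met with 800, 750 and even 600 patients, and at 26% it is still met with 750. The drop-out slip costs 50 evaluable patients, or about 0.1 point. The target is only approximate, and the intervals are declared exploratory and descriptive. All of this stands and sets the severity. It does not make the figures right.

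On clustering, a design effect used for sizing does not oblige a clustered variance in the analysis, and site and country variation is displayed elsewhere (SAP 8.7 and 8.8). That also stands, and it is why the clustered interval is offered only as an option.

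Several stronger readings are tempting, and the documents do not support them:
- **The registry is too small.** The main arithmetic error runs the other way.
- **The sponsor chose to drop the cluster allowance.** The documents are silent on clustering in the interval; they do not say it will be ignored.
- **The SAP sets a conflicting target.** Its 800 to 1000 can be read as evaluable to enrolled. It is loose wording.
- **The subgroup must have had exactly 196 patients.** That depends on how the printed figures were rounded.
- **The exclusions in SAP 4.2 and 8.1.1 cut the 750 further by a calculable amount.** No rate is given, and some may already count as drop-out, since ablation with another technology is a study-exit reason in Protocol 7.2.

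**Conclusion.** The point holds as a low-severity correction of the record. The plan's own inputs give ±3.04% (width 6.07%), not ±3.8%. A 25% loss from 1000 leaves 750, so the plan as written does not deliver 800 evaluable patients. The precision is attached to re-ablation, while the endpoint is AF recurrence, for which it would be about ±3.4% with 750 patients at an assumed 26%.

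Steps 1 to 5 rest only on stated inputs. The recurrence figures rest on assumed rates and treat the estimate as a simple proportion, which is approximate for a Kaplan-Meier analysis with censoring. The clustering effect, about 0.3 points per limit, rests on 1.2 being the true design effect.

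SAP version 1.1 is dated December 2018, after the tentative end of recruitment in Q2 2018. The correction therefore concerns documentation and does not call for more enrolment.

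**What to change.** In SAP 3.1 and 3.3, and in Protocol 4.3 by a clarifying note or at the next amendment:

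- Restate the precision as ±3.0% at 20% with n = 800, or ±3.1% with n = 750.
- Use one set of figures throughout: 1000 enrolled with 25% loss leaving 750, or 1000 enrolled with 20% loss leaving 800.
- Name AF recurrence as the planning outcome and give its precision, for example ±3.4% at an assumed 26% with n = 750.
- State the subgroup size behind ±6.6% (about 195 to 200 with design effect 1.2).

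The cost is rewording. A clarifying note avoids a stand-alone Protocol amendment, which would need the submissions and approvals described in Protocol 6.4 and 12. No patients are added.

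Optional sensitivity analysis in SAP 8.1.2: keep Greenwood as the headline interval and add one site-clustered 95% interval (delete-one-site jackknife or site bootstrap, log-log scale) for the 12-month Kaplan-Meier estimate in the Full Analysis Set only. The jackknife means about 38 to 40 refits, one per site. The added interval would be about 10% wider if the design effect is 1.2 (√1.2 = 1.095). Other analyses stay as planned.

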4.4.1 Statistical methods for the main objective

Estimate Phased RFA 12 months success rate

Rational: Previous studies have demonstrated that Phased RFA with the predicate platinum electrode catheter, PVAC, effectively isolates PVs with an average chronic efficacy of 74% with average follow up of 10 months. The Phased RFA literature meta-analysis published by Andrade, et al (19) reported comparable chronic success (6 months FU) was reported as 81.4% and 54.1% for paroxysmal and persistent AF, respectively.

The clinical effectiveness of PVAC GOLD catheter has yet to be estimated in PMR observational studies to establish if prospective interventional studies outcome is reproducible in daily clinical practice.

Main observational criteria: Success rate estimated as the time to first AF recurrence and/or left Afl and/or AT event from the index procedure. Data about AF events will be collected since the index procedure, including 90 days of the “blanking period” and closes at 12 months FU. If no AF/left Afl and/or events occur during the entire follow up period, 12 (+2) months, the case is considered to be “event-free”.

End point definition:

1. AF pharmacological and/or electrical CV
2. AF and or left Afl more the 30 sec on ECG/EGM
3. AF less than 30 sec in combination with AF symptoms
4. Re-ablations for AF
5. Ablations for left Afl or left AT

Analysis Methods: Freedom from AF recurrence at 12 months will be estimated using Kaplan-Meier methods. A point estimate at the date of 12 months FU post procedure will be presented. Standard error will be approximated using Greenwood's formula, and a two-sided 95% log-log confidence interval will be presented. Day 0 is defined at the date of index procedure. For patients with an AF recurrence, follow up time will be set to the date of recurrence. For patients without a reported AF recurrence, those patients will be censored at the last study contact date.

Limitations: Time to first AF recurrence has practical advantages as a primary endpoint, but does not accurately reflect clinically important parameters such as the frequency, type, and duration of AF recurrence and the overall AF burden. Above known, that significant percentage of patients has silent (or asymptomatic) AF and even more, the tendency to convert symptomatic form AF to asymptomatic after PVI.

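### The sample-size precision is stated for 20% re-ablations, not for 12-month AF recurrence; the printed ±3.8% does not follow from its inputs, and the subgroup guarantee is unsupported

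*Protocol*

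**What the plan says.** Protocol 4.3 begins from freedom from AF recurrence at 12 months and adds: "Efficacy in this case is assumed as the proportion of AF recurrence within 12 months following the index procedure". The only overall precision statement then changes the outcome. It reads "Assuming a prevalence of 20% of re-ablations 12 months after treatment", and on that basis "a sample size of 800 will allow the study to estimate the prevalence with a given precision of" ±3.8% (interval width 7.6%). The notes under Table 4-1 define precision as the half-width of a 95% interval and set a design effect of 1.2.

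SAP 3.3 repeats the table and the figures but names only the second outcome: "Efficacy is in this case assumed as the proportion of redo ablations 12 months after treatment".

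The main endpoint is wider in both documents. Protocol 4.4.1 counts the first of five event types, of which re-ablation for AF is the fourth. SAP 8.1.1 sets that definition aside and lists four, without the left flutter and left atrial tachycardia items; re-ablation for AF remains one of them.

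On subgroups, Protocol 4.3 says: "This size guarantees enough information for estimating the prevalence in smaller subgroups". Its example is a prevalence of 25% with ±6.6% (width 13.3%). It names no subgroup and gives no subgroup size.

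The rationale in Protocol 4.4.1 cites 74% success over an average of 10 months with the predicate catheter. It also cites 6-month success of "81.4% and 54.1% for paroxysmal and persistent AF, respectively".

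**The concern.** The registry tests no hypothesis, so expected precision is its only quantitative case for about 1000 patients. That case is made for one component of the main endpoint. Over the same patients and period, a composite cannot be rarer than one of its components, and below 50% a more frequent outcome has a wider interval. The Protocol's own rationale points to more recurrence than the 20% used: 26% overall and 45.9% in persistent AF.

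Persistent AF has its own ancillary objective, a predefined subgroup with 12-month scope (SAP Appendix C) and Kaplan-Meier curves by AF type (SAP 8.8). Neither document plans a number or a precision for it, and Table 4-1 stops at a prevalence of 0.3.

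**Working it through.** **Inputs.** Design effect 1.2, 95% two-sided interval, 800 evaluable, 25% drop-out and about 1000 enrolled (Protocol 4.3). Recurrence of 1 − 0.74 = 26% overall and 1 − 0.541 = 45.9% in persistent AF (Protocol 4.4.1).

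**Formulas.** Half-width h = 1.96 × √(1.2 × p × (1 − p) / n). Inverted, n = 1.2 × 1.96² × p × (1 − p) / h².

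**1. Table 4-1.** For p = 0.20 and h = 2.5%: 1.2 × 3.8415 × 0.16 / 0.025² = 1180.1, against 1181 printed. All 12 cells reproduce to within about two patients, so this is the plan's formula.

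**2. The printed ±3.8%.** For p = 0.20 and n = 800: 1.96 × √(1.2 × 0.16 / 800) = 3.04%. Other interval methods do not close the gap: Wilson gives 3.03%, Clopper-Pearson 3.11%, and a continuity correction 3.11%. Reaching 3.8% at p = 0.20 would take n = 511 or a design effect of 1.88. The printed figure does match p = 0.50: 1.96 × √(1.2 × 0.25 / 800) = 3.795%, width 7.59%.

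**3. AF recurrence overall.** The column for 750 is 1000 × (1 − 0.25).

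| Recurrence | n = 800 | n = 750 |
|---|---|---|
| 26% | ±3.33% | ±3.44% |
| 35% | ±3.62% | ±3.74% |
| 40% | ±3.72% | ±3.84% |
| 50% (worst case) | ±3.80% | ±3.92% |

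With 800 evaluable, ±3.8% holds at any rate. With 750 it holds until recurrence lies somewhere between 35% and 40%, and is then exceeded by at most about 0.1 percentage points. At 26%, ±3.8% needs 615 patients.

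**4. The subgroup example.** The ±6.6% is reproduced by p = 0.25 with n = 200 (a quarter of 800): 6.57%, although the width is then 13.15%, not 13.3%. The text does not say whether 25% is the event rate, the subgroup's share, or both.

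**5. Persistent AF at 45.9% recurrence.** The share is an assumption, because the documents plan none.

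| Share of 800 | n | Half-width |
|---|---|---|
| 20% | 160 | ±8.46% |
| 25% | 200 | ±7.57% |
| 30% | 240 | ±6.91% |
| 40% | 320 | ±5.98% |

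For ±6.6%: n = 1.2 × 3.8415 × 0.459 × 0.541 / 0.066² = 263, or 33% of 800.

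**The case against.** The strongest reply is that the main objective loses nothing. The only overall half-width in print is ±3.8%, and with 800 evaluable patients that is the largest the formula can give. Anyone who takes it as the precision of 12-month success gets a cautious figure. Table 4-1 also runs to a prevalence of 0.3, above the 26% in question. The registry is descriptive, and its main result will carry its own Greenwood-based interval. This stands: the documents do not show that the registry is too small.

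A reader might infer that the main-objective interval will be about a tenth wider than the plan states (3.33% against 3.04%). The documents do not support that, because the plan never prints ±3.04%.

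A reader might also set about ±8% for persistent AF against the plan's ±6.6%. That ±8% needs a share of about 22.6%, taken from a survey that Protocol 4.4.2 cites for safety (620 of 2,748 patients), and the ±6.6% is not tied to persistent AF. Above a share of about one third, ±6.6% is met.

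What the reply does not remove is the conflict over which outcome was sized, a figure that contradicts its own inputs, and a guarantee that depends on an unstated subgroup size.

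**Conclusion.** The concern holds as a mismatch of parameter and figure, not as a shortage of patients. The stated inputs give ±3.04% where ±3.8% is printed. That a rate of 50% was actually used is only an inference from the match. At an assumed 26% recurrence the half-width is ±3.3% for 800 patients and ±3.4% for 750, both inside the printed figure.

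The margin is accidental. If the figure were corrected to ±3.0% and the re-ablation assumption kept, the plan would then overstate its precision for AF recurrence. The parameter and the figure should be corrected together.

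The word *guarantees* is unsupported for subgroups. At 45.9% recurrence, shares of 20% to 40% give about ±8.5% to ±6.0%.

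These results assume that the binomial formula is a fair proxy for the planned Kaplan-Meier interval, for which no design effect is mentioned. They also assume that rates cited at 6 months and at an average of 10 months can stand in for 12 months; true 12-month recurrence may be higher.

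**What to change.** In Protocol 4.3 and SAP 3.3:

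- Name 12-month AF recurrence, as finally defined, as the parameter, and drop the re-ablation assumption.
- Replace ±3.8% at 20% with half-widths at design effect 1.2. At 26% recurrence (labelled as an assumption from 74% success at an average of 10 months) these are ±3.3% for 800 and ±3.4% for the 750 left from 1000 after 25% drop-out. Give the 50% worst cases of ±3.8% and ±3.9% beside them.
- Replace the subgroup guarantee with half-widths conditional on size. For persistent AF at 45.9% (labelled as a 6-month figure) these are about ±8.5%, ±7.6%, ±6.9% and ±6.0% at shares of 20%, 25%, 30% and 40% of 800, with ±6.6% needing about 263 patients. State that the share is assumed.

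The cost is a rewording of two short sections and a less favourable stated subgroup precision. Enrolment does not change.
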